1.3 Clinical Study Experience

This study represents the first clinical trial on the Apollo™ micro catheter. The device was approved for commercialization in the European Union in 2009.

Two key clinical studies have reported on the use of Onyx™ LES: 1) a prospective randomized controlled trial comparing Onyx™ LES with NBCA and 2) an international prospective, multicenter registry. These studies are summarized below.

1.3.1 Randomized Controlled Trial of Onyx™ LES vs. NBCA

In 2001 a prospective, equivalence, multicenter, randomized controlled trial was initiated to verify the safety and efficacy of Onyx™ LES compared with NBCA for the pre-surgical treatment of brain AVMs. Loh et al. reported on the pivotal trial for Onyx™ LES on behalf of the trial Investigators.³⁹

The analysis included 117 Subjects with brain AVMs who were randomized and treated with either Onyx™ LES (54 Subjects) or NBCA (63 Subjects) for pre-surgical endovascular embolization between May 2001 and April 2003. Technical success in achieving a ≥50% reduction in AVM volume was the primary endpoint. Secondary endpoints were operative blood loss and resection time. All adverse events (AEs) were collected and assessed for relationship to the Onyx™ LES or NBCA system, treatment, disease, surgery or other/unknown. The Data Safety Monitoring Board adjudicated AEs, and a blinded, independent core lab assessed volume measurements. Study Subjects were followed through discharge after the final surgery or, if resection was not performed or was incomplete, Subjects were followed through 3- and/or 12-month follow-up.

Technical success in achieving a ≥50% AVM volume reduction with Onyx™ LES was achieved in 96% of cases versus 85% of cases with NBCA (p=NS). The secondary endpoints of resection time and blood loss as well as serious AEs were similar between treatment groups. System-related serious AEs during treatment with Onyx™ LES included 3 cases of neurological decline, including cranial neuropathy with permanent deficit and transient paresis post-embolization following difficult catheter removal; worsening seizures and neurological decline related to contrast extravasation from ruptured catheter shaft, bilateral retinal hemorrhages caused by increased intracranial pressure, and transient hemiparesis and hemianopia; and difficult catheter removal and vasospasm with prolonged hospitalization for significant but transient deficits. One stroke with permanent deficit occurred following embolization of unintended vessel and subsequent infarction. One intracranial hemorrhage caused by catheter rupture and resulting in permanent deficit occurred. One vessel dissection was noted at the time of second embolization which was presumably from the first embolization procedure; the vessel was stented for moderate stenosis. Technical and procedural events included: difficulty removing catheter (n=6), rupture of delivery catheter (n=2), failed access (n=9), fragmentation of Onyx™ (n=1), poor penetration/visualization (n=6), small amount of Onyx™ in vein (n=1), vasospasm (n=1), vessel dissection (n=1), and laboratory/imaging abnormalities (n=6). The Investigators concluded that Onyx™ LES is equivalent to NBCA in safety and efficacy as a preoperative embolic agent in reducing brain AVM volume by at least 50%.

1.3.2 BRAVO Registry

An international, prospective, multicenter registry (BRAVO) was conducted to evaluate the safety and performance of Onyx™ LES in the treatment of brain AVMs until treatment completion. The primary efficacy endpoint was the AVM occlusion rate at the end of all Onyx™ treatment sessions

measured by angiography and evaluated by an independent core laboratory. The primary safety endpoint was rate of Subject morbidity and mortality. Pierot *et al.* reported on the results of the BRAVO registry.⁴⁰

A total of 123 Subjects were enrolled in the registry. Six Subjects were excluded due to not meeting the inclusion/exclusion criteria (2 were <18 years old, 3 had dural fistula, and 1 had been previously treated for AVM). One hundred seventeen (117) Subjects were included in the analyses. The average age was 42.6 ± 13.6 years with 61.5% male. Clinical presentation was primarily hemorrhage (34.2%) and seizures (28.2%). The size of the AVMs was <3 cm for 52.1% of Subjects and ≥ 3 cm for 47.9% of Subjects. Following all Onyx™ LES treatments, the degree of occlusion was 100% for 23.5% of Subjects, 75-99% for 33.9%, 50-75% for 27.8% and <50% occlusion for 14.8% of Subjects. For Subjects with smaller AVMs <3 cm, the 100% occlusion rate was 37.7%. The treatment-related mortality rate was 4.3%, including 4 deaths due to bleeding and 1 death due to an extensive venous thrombosis. The treatment-related morbidity rate was 7.1% with morbidity due to bleeding for 4 cases and due to other causes for 4 cases. Treatment-related hemorrhage occurred in 12.8% of Subjects. Other treatment-related serious adverse events included left hemiplegia with residual deficit, pneumopathy, dysmetry right deficit with residual deficit, venous thrombosis resulting in death, and two access site complications. The Investigators concluded that Onyx™ LES “proved to be suitable for brain AVM embolization, with acceptable morbidity and mortality and good efficacy.”

1.4 Rationale of Clinical Study

Although endovascular embolization of brain AVMs with Onyx™ LES is performed regularly, catheter entrapment/abandonment is a complication that has been reported in up to 10% of Subjects treated with Onyx™ LES.^{10,12,15,16,18,19} In order to help prevent catheter entrapment/abandonment, the Apollo™ micro catheter was designed with a detachable distal tip that allows for catheter retrieval. This device was approved for commercialization by the Food and Drug Administration on May 27th 2014 for the controlled selective infusion of Onyx™ LES. The present study aims to evaluate the safety of the Apollo™ micro catheter through the assessment of catheter-related AEs and long-term follow-up of Subjects in whom the catheter tip/body is retained.

1.4.1 Study Population

A total of 161 Subjects will be enrolled into this study and are expected to contribute data on an estimated 322 Apollo™ micro catheter utilizations (e.g., approximately 2 catheters used per Subject). Males or females with a confirmed diagnosis of a brain AVM will be eligible for participation in the study if they satisfy the inclusion and exclusion criteria. The Apollo™ micro catheter will be used to deliver Onyx™ LES to eligible Subjects for either presurgical embolization of brain AVMs or for the embolization of brain AVMs without subsequent surgery. This patient population has been selected in order to collect post-approval data on the safety of the Apollo™ micro catheter when used by a broad group of physicians under commercial use conditions.

1.4.2 Single-Arm Study Design

The proposed study design is a prospective single-arm multicenter trial to evaluate the use of the Apollo™ micro catheter to deliver Onyx™ LES during AVM embolization procedures. A single-arm design was selected since the incidence rates associated with catheter retention are published in the literature and can be used to define objective performance criteria. Furthermore, there are no alternative micro catheters that could form a reasonable concurrent control group. There is only one other micro catheter with a detachable tip (Sonic Micro Catheter, Balt Extrusion), however, it is not approved for use in the United States.

1.4.3 Conclusion

In summary, left untreated, brain AVMs are potentially life-threatening and are associated with significant morbidity and mortality. Treatment of AVMs with liquid embolics such as Onyx™ LES can result in avoidance of AVM rupture and minimizes intraoperative blood loss during surgical resection of the AVM, thereby reducing morbidity and mortality. Although these rates are reduced compared to those for AVMs left untreated, treatment with liquid embolics could lead to catheter entrapment. Use of the Apollo™ micro catheter has the potential to decrease the incidence of this complication.

Thus, the aim of the present study is to assess the safety of the Apollo™ micro catheter used for delivery of the Onyx™ LES during brain AVM embolization procedures.

2 DEVICE DESCRIPTION

2.1 Intended Use

The Apollo™ micro catheter is intended to access the neuro vasculature for the controlled selective infusion of the Onyx™ LES.

2.2 Device Name

Apollo™ micro catheter is used to deliver the Onyx™ LES, which received PMA approval in the US in 2005. Onyx™ LES is available in the United States in two formulations: Onyx™ 18 LES and Onyx™ 34 LES. Onyx™ 18 LES contains 6% EVOH and Onyx™ 34 LES contains 8% EVOH. Onyx™ 18 LES will travel more distally and penetrate deeper into the nidus due to its lower viscosity compared to Onyx™ 34 LES.

[figure not shown]
2.3 Device Description

The Apollo™ micro catheter is a single-lumen, endhole catheter intended to access the neurovasculature for the controlled selective infusion of Onyx™ LES. The catheter has a semi-rigid proximal shaft and a highly flexible distal shaft to facilitate the advancement of the catheter in the anatomy. The proximal end of the catheter incorporates a standard luer adapter to facilitate the attachment of accessories. The outer surfaces of the catheter are coated to increase lubricity.

The Apollo™ micro catheter is designed to facilitate catheter retrieval in the event the catheter becomes entrapped within the Onyx™ LES cast. The distal section of the catheter incorporates a detachment

zone that allows detachment of the distal tip when the force required to extract the catheter exceeds the force required to detach the tip (Figure 1). The catheter has two radiopaque marker bands to visualize the position of the catheter and the detach zone area (Figure 2):

- Proximal to the detach zone
- At the distal end of the detachable tip (distal end of catheter)

REF*	A	B-Tip Length	C	D
105-5095-000	0.5 mm	1.5 cm / 15 mm	1.25 mm	1.9 F / 0.63 mm
105-5096-000	0.5 mm	3 cm / 30 mm	1.25 mm	1.9 F / 0.63 mm

*Table indicates micro catheter dimensions. Letters A, B, C, and D listed in the table correspond to the sections/points labeled on the figure.

Figure 1. Apollo™ Onyx™ Delivery Micro Catheter Dimensions

[figure not shown]

Figure 2. Marker bands of Apollo™ Onyx™ Delivery Micro Catheter

2.4 Device Labeling

The Apollo™ micro catheter is an approved, commercially available device. However, this device is being investigated for the potential safety effects of retaining the catheter tip in the neurovasculature.

2.5 Device Tracking

The lot number of each Apollo™ micro catheter will be captured on the case report forms. Due to commercial availability, all shipments will not be tracked for the study.

2.6 Devices and Equipment

In addition to Onyx™ LES and the Apollo™ micro catheter, devices that may be required for the study procedure include (but are not limited to) those listed below. All devices required to perform the procedure will be provided by the site.

- Access devices: Guiding catheter and sheath
- Non-ionic contrast
- Guidewires
- Any other adjunctive, approved/cleared device for AVMs

The Onyx™ delivery procedure is described in detail in the Instructions For Use (IFU) document.

Note: The Investigator will undergo training on the use of the Apollo™ micro catheter and on the IFU prior to performing any Onyx™ delivery procedures with the Apollo™ micro catheter in this clinical study.

3 STUDY OBJECTIVES

3.1 Primary Composite Endpoint (30 days)

- Incidence of catheter-related AEs per Subject:
 - Premature (unintentional) catheter tip detachment with clinical sequelae*
 - Catheter rupture/break/fracture with clinical sequelae*, and
 - Retained catheter body in the vasculature.

*Clinical sequelae are defined as all focal neurologic deficits related to lesions within the vascular territory catheterized. Vascular territory catheterized is defined as the brain tissue supplied by the vascular tree selectively catheterized using the Apollo™ micro catheter.

3.2 Acute Secondary Endpoints (30 days)

- Rate of premature (unintentional) catheter tip detachment
 - Unintentional tip detachment is defined as detachment of the catheter tip within the vasculature at an unintended location.
- Rate of intentional catheter tip detachment
 - Intentional catheter tip detachment is defined as deliberately applying the necessary force on the catheter to detach catheter tip.
- Rate of migration of the retained catheter tip post embolization
- Incidence of procedure-related AEs
- Rate of catheter/tip leakage from detachment zone

3.3 Long-Term Secondary Endpoints (12 months)

- Incidence of AEs
- Rate of migration of the detached catheter tip post embolization

Incidence is defined as the cumulative number of endpoint events divided by the total number of embolizations completed in the study.

Migration is defined by an observed change in position of the detached tip during imaging or by discovering the detached tip at some location other than the one identified at the last imaging.

4 STUDY DESIGN

4.1 Study Design and Projected Timeline

This study is a prospective, single-arm, multi-center, post market safety evaluation of Subjects indicated for embolization of brain AVMs with Onyx™ LES, delivered with the Apollo™ micro catheter.

The projected timeline for this study is as follows:

Expected date of study initiation:

Expected monthly number of study sites with IRB approvals:

Expected number of subjects enrolled per month:

Expected date of enrollment completion:

Expected date of study follow-up completion:

Expected date for Final Report submission:

4.2 Number of Sites and Subjects

Up to 161 Subjects with an estimated 322 catheter utilizations (~2 catheters per Subject) will be enrolled in this study from up to 25 US sites.

4.3 Study Population

Subjects with a brain AVM indicated for embolization with Onyx™ LES using the Apollo™ micro catheter will be enrolled in this study.

4.4 Subject Selection Criteria

Waivers will not be granted by the Sponsor regarding Subject inclusion/exclusion criteria.

4.4.1 Inclusion Criteria

1. The Subject or Subject's legally authorized representative has signed and dated an informed consent form.
2. The Subject has a confirmed diagnosis of a brain AVM.
3. The Subject is clinically and neurologically stable for a minimum of 48 hours prior to embolization.
4. The Subject has a life expectancy of at least 1 year.
5. The Subject agrees to and is capable of completing all study-required procedures.

4.4.2 Exclusion Criteria

1. Current participation in another investigational drug or device study that evaluates treatments for brain AVMs or other cerebrovascular disease.
2. The Subject has a bleeding disorder.
3. The Subject is not a candidate for the use of vasodilators.

5 STUDY PROCEDURES

5.1 Overview of Study Flow

A representative overview of the study flow is shown below.

[figure not shown]

Figure 3. Study Flow

5.2 Informed Consent and Privacy

A thorough explanation will be provided to the Subject (or legally authorized representative) as to the nature and objectives of this study. Details of the study should include (but are not limited to) the following terms:

- Purpose of the study
- Alternative treatments
- Need to return for 30-day, and 12-month visits
- Participation is voluntary, and there is no penalty for withdrawal
- Potential risks/benefits for participation
- Contact information to ask questions or voice concerns

The study Investigator and/or staff are responsible for obtaining written informed consent from each potential Subject. Informed consent should be obtained in written format and using a form approved by the local IRB. The form should contain standard language consistent with local policies for ensuring privacy of confidential information. All Subjects must sign the informed consent form (ICF) prior to any procedures/tests that go beyond initial assessments associated with the standard care for Subjects with AVMs and before any study-related treatments assessments are administered.

It is the responsibility of the Investigator to give each Subject (or Subject's legally authorized representative) prior to inclusion in the study, full and adequate verbal and written information regarding the objective of this study and the confidentiality of the data collected.

5.3 Screening

Subject eligibility assessment is to be performed based on data available to the Investigator at the time of screening. This initial screening phase may include review of existing Subject information (previously performed angiography, radiographs, laboratory studies, medical history, physical examination, etc.) and referral to the treating physician. Subjects must comply with all inclusion and exclusion criteria. Waivers will not be granted by the Sponsor regarding Subject inclusion/exclusion criteria.

All Subjects screened should be included on the study screening log. The reason of non-eligibility for all Subjects who are deemed ineligible by the Investigator should also be recorded on the study screening log. The screening log serves as a method for Covidien to ensure that there is no selection bias in the trial.

5.3.1 Schedule of Assessments

An overview of the assessments to be performed is provided in Table 1.

Table 1. Schedule of Assessments

Assessment	Baseline (-30 days)	Pre- Embolization	Embolization Procedure	Post- Embolization Discharge or +24 hours post- embolization	Surgical Resection	30 Day Follow-up ¹ (+/-7 days)	12 Month Follow-up ² (+/-42 days)
Informed Consent	♦						
Inclusion/Exclusion	♦						
Demographic Characteristics	♦						
Medical History	♦						
Brain AVM characteristics	♦						
Physical Exam	♦						
Neurologic Exam	♦						
Barthel Index		♦		♦		♦	♦
Modified Rankin Scale (mRS)		♦		♦		♦	♦
National Institutes of Health Stroke Scale (NIHSS)		♦		♦		♦	♦
Imaging	•	♦	♦	♦	♦	♦ ³	♦
Embolization Procedure Information and Device Usage or Surgical Resection			♦	♦	♦		
Technical Events			♦				
Concomitant Medications	•	♦	♦	♦	♦	♦	♦
Adverse Events			♦	♦	♦	♦	♦

1. 30 day follow-up will occur 30 days after surgical resection, or 30 days after initial embolization if resection is not done.

2. Only for Subjects with catheter and/or catheter tip retention. If the Subject has had multiple embolization procedures, the 12-month visit will take place 12 months after the initial embolization procedure.

3. Subjects with catheter and/or catheter tip retention, or based on physician assessment.

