If the catheter and/or tip are retained (intentionally or unintentionally) during the initial procedure or any subsequent procedures, the Subject will be followed for 30 days from the date of the initial procedure to assess any adverse events ascribed to the study procedure or the retained catheter or tip. For Subjects where surgical resection of the Onyx™ cast and retained catheter tip is not undertaken or is incomplete and the catheter and/or tip are retained (intentionally or unintentionally), the Subject will also complete a 12-month follow-up visit to assess safety. Once a Subject has completed the study procedures, all ongoing adverse events will be followed until resolution or until event has stabilized.	

PROTOCOL SYNOPSIS

Sponsor:	Protocol Number: NV-APL001
Micro Therapeutics, Inc. d/b/a ev3 Neurovascular [name]	Revision: A, 05-Aug-2014
	Product: Apollo™ Onyx™ Delivery Micro Catheter
	Regulatory Class: Class III
	Development Phase: Phase IV

Study Flowchart:

PROTOCOL SYNOPSIS	
Sponsor: Micro Therapeutics, Inc. d/b/a ev3 Neurovascular [name]	Protocol Number: NV-APL001
	Revision: A, 05-Aug-2014
	Product: Apollo™ Onyx™ Delivery Micro Catheter
	Regulatory Class: Class III
	Development Phase: Phase IV

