5.11 Follow-up Evaluations

5.11.1 30-Day

Subject who underwent surgical resection will complete a 30-day visit 30 days after surgical resection. For Subjects not undergoing surgical resection, the 30 day visit will be performed 30 days after the initial study embolization. Table 1 describes a list of assessments that will be performed at this visit. Subjects with a retained catheter/tip will undergo imaging at this time point. Subjects experiencing AEs may undergo imaging per physician discretion. Subjects not experiencing an AE and in whom no part of the catheter was retained will complete the study. Subjects experiencing an AE and in whom no part of the catheter was retained will continue to be followed up until AE resolution.

5.11.2 12-Month

Subjects in whom a catheter and/or tip were retained will have a 12-month study visit. If the Subject has had multiple embolization procedures, the 12-month visit will take place 12 months after the initial embolization procedure. If the Subject is experiencing ongoing AEs at 12 months, the Subject will be followed until resolution of the AE. The clock will only reset, if during re-treatment the catheter tip detaches in a non-target location and is not resected. Final imaging will be required at this visit. Table 1 describes a list of assessments that will be performed at this visit.

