8.2 Imaging Core Laboratory

For Subjects in whom the catheter or catheter tip is retained, 30-day, and 12-month imaging will be obtained to assess potential catheter tip migration. Thirty-day imaging will also be collected if it is performed as a result of physician discretion.

Any subsequent imaging obtained as standard of care during participation in the study will be documented on the eCRFs and may be collected.

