9.2.6 Analysis of Secondary Endpoints

For acute and long-term secondary endpoints, descriptive statistics will be provided. Event rates based on Subject count and device count will be provided.

The incidence of catheter and / or tip retention following any deployment of the study device will be summarized using counts, percentages, and 2-sided 95% exact binomial confidence intervals.

Separately, the incidence of catheter and tip retention by the number of deployments of the study device will be summarized using counts, percentages, and 2-sided 95% exact binomial confidence intervals. This tabulation assumes that each procedure / deployment is a separate trial. The intra-subject rate of catheter and tip entrapment will be summarized using descriptive statistics and tabulated by the number of events and the number of deployments.

In order to ensure a sufficient number of cases for long-term follow-up, the expectation is that with 161 subjects enrolled there will be approximately 16 to 26 subjects with 1-year follow-up. The basis of this estimate is that approximately 50% to 80% of the subjects will have the tip retained by design and approximately 20% of these subjects will not undergo surgery and shall be followed for 1-year. Any retained catheter bodies will be followed. Relative to the precision of the estimates with 16 subjects followed for 1 year, if the incidence of composite primary endpoint events is zero or 1, the exact upper 1-sided Clopper-Pearson 95% limit would be 17.07% and 26.40%, respectively. If the incidence of composite primary endpoint events with 26 subjects was zero or 1, the exact upper 1-sided Clopper-Pearson 95% limit would be 10.88% and 16.98%, respectively.

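### The 30-day migration image follows resection in operated Subjects, so it cannot show earlier movement of a removed tip (up to about 80% of retained tips), and section 8.2 routes no other image to the acute reading

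*Combined protocol and SAP*

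**What the plan says.** Section 3.2 lists, among the acute (30-day) secondary endpoints, "Rate of migration of the retained catheter tip post embolization". Section 3.3 defines migration as a change in tip position seen on imaging, or as finding the tip somewhere other than where the last imaging placed it. Section 8 gives the assessment of device migration to the Imaging Core Laboratory. Section 8.2 says which images serve it, for Subjects with a retained catheter or tip: "30-day, and 12-month imaging will be obtained to assess potential catheter tip migration". Other imaging done as standard of care is documented and may be collected.

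Footnote 1 to Table 1 (section 5.3.1) fixes the visit: "30 day follow-up will occur 30 days after surgical resection, or 30 days after initial embolization if resection is not done". Section 5.11.1 agrees: "Subject who underwent surgical resection will complete a 30-day visit 30 days after surgical resection". Footnote 3 limits 30-day imaging to Subjects with a retained catheter or tip, or to the physician's judgement. Table 1 also marks imaging at the embolization procedure, at discharge or +24 hours, and at surgical resection. Section 5.10 collects imaging, the degree of resection and catheter retainment at surgery.

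The synopsis (Follow-up) uses another origin when a catheter or tip is retained: "the Subject will be followed for 30 days from the date of the initial procedure".

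Section 9.2.1 reports secondary endpoints as Subjects with an event over the total number of Subjects in the analysis population. On expected numbers, section 9.2.6 puts tip retention at 50% to 80% of Subjects. Of that group, it expects that "approximately 20% of these subjects will not undergo surgery and shall be followed for 1-year".

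**The concern.** For a Subject who goes on to surgery and whose tip is taken out, the tip is at risk of moving only between embolization and resection. The 30-day image is taken about 30 days after that period has ended. It cannot show what happened to a tip that is no longer there.

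Footnote 3 does not resolve this. If retention means still retained, a fully resected Subject needs no 30-day image. If it means ever retained, the image is taken but says nothing about a removed tip. Either way, the only images that section 8.2 assigns to the acute reading leave such Subjects without an informative assessment.

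The analysis section does not provide for that. It has no evaluability rule for migration, and section 9.2.9 discusses missing data for the primary endpoint only. Under the section 9.2.1 denominator, a Subject never assessed for migration is counted as having had none. Section 2.4 says the device is under study for the safety effects of a tip left in the neurovasculature, so a migration rate that looks low because it was not measured would mislead on a question this study is meant to inform.

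**Working it through.** **Inputs.** From section 9.2.6: 161 Subjects enrolled; 50% to 80% with a retained tip; about 20% of these without surgery, hence about 80% with surgery.

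**Step 1: reproduce the plan's figures.**
- Retained tip, no surgery: 161 × 0.50 × 0.20 = 16.1 and 161 × 0.80 × 0.20 = 25.8. These match the stated 16 to 26.
- One-sided exact 95% upper limits: 17.07% for 0/16, 26.40% for 1/16, 10.88% for 0/26 and 16.98% for 1/26. All four match section 9.2.6.

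**Step 2: Subjects whose 30-day image follows surgery.**
- Retained tips: 161 × 0.50 = 80.5 and 161 × 0.80 = 128.8, about 81 to 129.
- Operated: 80.5 × 0.80 = 64.4 and 128.8 × 0.80 = 103.0, about 64 to 103.

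**Step 3: share whose tip is gone by then.** The 80% is the share expected to have surgery. Let q be the share of operated Subjects in whom the tip stays in place; the documents give no value, so q is an assumption. The share of retained-tip Subjects with the tip gone is 0.80 × (1 − q):

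| q | Tip gone at the 30-day image |
|---|---|
| 0 | 80% |
| 0.1 | 72% |
| 0.2 | 64% |
| 0.5 | 40% |

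**Step 4: effect if unassessed Subjects count as non-events.** Assume complete removal (q = 0), the same migration risk m in operated and unoperated Subjects, and no use of any other image. Events are then seen only in the unoperated 20%, so the reported rate among retained-tip Subjects is 0.20 × m. A true 5% is reported as 0.20 × 5% = 1%. The factor of one fifth is the same whether the denominator is retained-tip Subjects or the whole analysis population, because only the numerator loses events.

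**Step 5: effect if resected Subjects are left out instead.** The rate then rests on 16 to 26 Subjects. With no events, the one-sided exact 95% upper limit is 1 − 0.05^(1/n):
- n = 16: 17.07%; n = 26: 10.88%.
- If all retained-tip Subjects could be assessed, n = 81: about 3.6%; n = 129: about 2.3%.

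**Step 6: time origin.** The synopsis counts 30 days from the initial procedure when a tip is retained. Table 1 footnote 1 and section 5.11.1 count from resection for operated Subjects. Both cannot hold for a retained-tip Subject who has surgery on a later day than the initial procedure.

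**The case against.** A reader might infer that migration cannot be seen at all in about 80% of retained-tip Subjects. The documents do not support that, for four reasons.

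- **Other images exist.** Table 1 schedules imaging at embolization, discharge or +24 hours, and resection. The section 3.3 definition is not tied to the 30-day visit, and a displaced tip found at surgery would meet it. Section 8.2 does not say that other images are excluded.
- **80% is a ceiling.** It is the share expected to have surgery. The synopsis and section 5.10 allow for incomplete or partial resection. That the tip is normally gone is an inference, not a statement in the plan.
- **The one-fifth figure is not a forecast.** Operated Subjects have a shorter period at risk, so equal risk is doubtful. A tip that had left the cast might not be removed with it and could still appear after surgery. No passage expressly says that resected Subjects are to be scored as not migrated, and the word retained could be read as excluding them.
- **The synopsis sentence concerns adverse events.** It does not schedule the migration image.

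All four stand as limits on the claim. They do not remove it. Detection is possible, but nothing says that the resection image precedes resection, locates the tip or reaches the core laboratory. Section 5.10 captures catheter retainment, not tip position. The discovery route needs a recorded earlier location, and section 8.2 does not send the core laboratory an end-of-procedure image. If resected Subjects are excluded, the dilution goes but the estimate rests on the small unoperated group of step 5.

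**Conclusion.** The concern holds in limited form. Where surgery removed the tip, the scheduled 30-day image cannot show movement before surgery. This affects up to about 80% of retained-tip Subjects, that is up to about 64 to 103 of 81 to 129, and fewer to the extent that resection leaves the tip in place. Because no other image is assigned to the reading and the stated denominator is all Subjects, the acute migration rate would be biased towards zero. One fifth of the true rate is the illustrative worst case, resting on complete removal, equal risk and no use of other images.

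Separately, the synopsis and Table 1 with section 5.11.1 give different origins for the 30 days and must be reconciled.

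Migration is a secondary endpoint analysed descriptively. The primary endpoint and the 9.6% performance goal are unaffected. The change should be made, but the study's main conclusion does not depend on it.

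**What to change.** - **Section 8.2.** Have the core laboratory use images already scheduled in Table 1. The end-of-procedure or discharge/+24-hour image is the position reference. For operated Subjects, the acute reading is the last available image before resection, later than the reference, together with any tip location recorded at surgery. The 30-day image is used for tips still in place. Record the date of each image read, so that the interval covered is known.
- **Sections 9.2.1 and 9.2.6.** Report the acute migration rate over retained-tip Subjects with an evaluable reading. List operated Subjects without one as not assessed, and give their number beside the rate.
- **Synopsis, Table 1 footnote 1 and section 5.11.1.** Reconcile the origin of the 30 days.

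Do not require new pre-operative imaging, and do not replace any image that documents the degree of resection. The plan does not say that the resection image precedes surgery, so making it a pre-operative image could add a procedure.

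**Cost.** Protocol and core-laboratory wording, plus uploading and reading up to about 64 to 103 existing image sets from operated Subjects, and reference images for the 16 to 26 not operated. The rate will be less precise if some operated Subjects prove not assessable, but their number will then be visible.
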